#### 9.5.13.8 *Bone Marrow Aspirate*

Bone marrow samples will be collected as specified in [Appendix A](#).

#### 9.5.13.9 *Local Laboratory Evaluations*

##### 9.5.13.9.1 *Disease Assessment*

A BMA will be obtained at screening for disease assessment and at any time during treatment to assess CR or to investigate suspected progressive disease if it is in accordance with standard local practice. This evaluation will be performed locally. Clonality for sCR should be established by showing κλ light-chain restriction on flow cytometry, immunohistochemistry, or immunofluorescence in bone marrow ([Appendix E](#)).

##### 9.5.13.9.2 *Cytogenetics*

The most recent cytogenetic results from samples taken between diagnosis and before study enrollment will be requested as part of medical history of the patients. The historical cytogenetic evaluation should have been analyzed locally, according to local standards, if the site has the capability to perform analysis using methodologies such as fluorescence in situ hybridization and/or conventional cytogenetics (karyotype).

All patients should also have a sample from screening sent for central analysis (BMA for cytogenetics).

#### 9.5.13.10 *Central Laboratory Evaluations*

##### BMA for MRD

For all patients, a BMA for MRD sample to determine rate and duration of MRD negativity should be collected at screening at the same time as the BMA and biopsy procedure is performed for local disease assessment purposes. Additionally, when a CR is suspected based on laboratory values, per routine clinical practice ([Appendix E](#)), a BMA should be drawn for local disease assessment and central analysis of MRD. Additionally for patients with a confirmed CR, BMAs for MRD should be collected at 6, 12, and 24 months following CR confirmation. If a patient has an MRD[-] result for any of the on-treatment assessments, this will trigger yearly evaluations of MRD, until the patient progresses. However, if a patient does not have an MRD[-] result for any of the planned on-treatment assessments, no additional BMA for MRD will be required. These evaluations will be performed at a central laboratory.

##### BMA for Cytogenetics

During the screening period, an additional 3 mL pull of bone marrow (fresh BMA) will be collected, on completion of the BMA for MRD sample collection, to centrally analyze a broad spectrum of cytogenetic abnormalities and [REDACTED], perform immunoprofiling, [REDACTED], [REDACTED], and plasma biomarker evaluation. Where country guidelines and/or regulations prohibit genomic analysis, a fluorescent in-situ hybridization will be used to evaluate

cytogenetic abnormalities and remaining biomarker assessments limited to immunoprofiling and plasma analysis.

[REDACTED]

[REDACTED]

[REDACTED]

[REDACTED]

[REDACTED]

[REDACTED]

[REDACTED]

[REDACTED]

### 9.5.14 Biomarker, PD, and PK Samples

#### 9.5.14.1 Primary Specimen Collection

Table 9.e summarizes primary specimen collection for the study.

Blood samples will be collected via venipuncture or indwelling catheter at the time points detailed in the SOE ([Appendix A](#)) for serum concentration measurements of modakafusp alfa ([Appendix B](#)) and biomarker assessments. Bone marrow biopsy and aspirate collections are specified in the SOE ([Appendix A](#)).

Details on sample handling, storage, shipment, and analysis are provided in the laboratory manual.

**Table 9.e Primary Specimen Collection**

Specimen Name	Primary Specimen	Primary Specimen Derivative	Description of Intended Use	Sample Collection
Serum sample for modakafusp alfa PK	Blood	Serum	Modakafusp alfa concentrations	Mandatory a
Serum sample for daratumumab PK	Blood	Serum	Daratumumab concentrations	Mandatory a
BMA for MRD	BMA	DNA	Biomarker measurements	Mandatory a
BMA for cytogenetics	BMA	DNA, RNA, plasma and immune cells	Biomarker measurements	Mandatory a
[REDACTED]				
Serum sample for immunogenicity	Blood	Serum	Immunogenicity measurement (ADA and NAb)	Mandatory
Blood sample for flow cytometry	Blood	N/A	Biomarker measurements	Mandatory
Serum sample for circulating biomarkers	Blood	Serum	Biomarker measurements	Mandatory
Blood sample for RNA	Blood	RNA	Biomarker measurements	Mandatory a
[REDACTED]				

ADA: antidrug antibody; BMA: bone marrow aspirate; MRD: measurable (minimal) residual disease; NAb: neutralizing antibody; PK: pharmacokinetics.

a Mandatory unless local regulations prohibit.

#### 9.5.14.2 PK Sampling

Details regarding the preparation, handling, and shipping of the PK samples are provided in the laboratory manual. Serum samples for PK will be collected at the time points specified in [Appendix B](#).

The timing, but not the total number of samples, may be modified during the study on the basis of emerging PK data if a change in sampling scheme is considered necessary to better characterize the PK of modakafusp alfa and/or daratumumab.

#### 9.5.14.3 [REDACTED]

#### 9.5.14.3.1 [REDACTED]

Topic	Percentage
Healthcare	98
Technology	95
Finance	92
Politics	88
Entertainment	85
Science	82
Food	78
Sports	75
Business	72
Art	68
History	65
Geography	62
Mathematics	58
Chemistry	55
Physics	52
Biology	48
Spanish	45
French	42
German	38
Japanese	35
Korean	32
Chinese	28
Arabic	25
Russian	22
Swahili	18
Portuguese	15
Urdu	12
Hindi	10
Malay	8
Turkish	5
Armenian	3
Georgian	2
Ukrainian	1
Other	1

9.5.15 [REDACTED]

[REDACTED]

[REDACTED]

[REDACTED]

[REDACTED]

**CONFIDENTIAL**

[REDACTED]

### **9.5.16 Immunogenicity Sample Collection**

Serum samples prepared from blood for assessment of immunogenicity will be collected at time points specified in the SOE ([Appendix A](#)) and as outlined in the laboratory manual. Samples must be collected before either study drug is administered on a dosing day, and it is strongly suggested that samples be obtained at unscheduled visits for a subject who experiences Grade  $\geq 2$  hypersensitivity/IRR (Section [8.10.1.1](#)). Samples confirmed ADA positive against modakafusp alfa will be assayed for the ADA titer and domain specificity characterization as well as their neutralizing ability. If serum PK samples from the modakafusp alfa in combination with daratumumab SC indicate a loss of detectable daratumumab PK, ADA against daratumumab may be evaluated as sample volume supports. [REDACTED]

[REDACTED]. These samples will be analyzed at a central laboratory ([Appendix A](#)).

### **9.6 Completion of Study Treatment (for Individual Patients)**

Patients will be considered to have completed study treatment if they discontinued study drug for any reason outlined in Section [9.8](#). Investigators are expected to evaluate the impact to the safety of the study participants and site personnel for subjects to continue. In evaluating such requests, the sponsor will give the highest priority to the safety and welfare of the subjects. Subjects must be willing and able to continue taking study medication and remain compliant with the protocol.

### **9.7 Completion of Study (for Individual Patients)**

Patients will be considered to have completed the study if they withdrew from the study for any reason outlined in Section [9.9](#).

### **9.8 Discontinuation of Treatment With Study Drug and Patient Replacement**

Study drug must be permanently discontinued for patients meeting any of the following criteria:

- Patient experiences an AE or other medical condition that indicates to the investigator that continued participation is not in the best interest of the patient.

Treatment with study drug may also be discontinued for any of the following reasons:

- AE.
- Protocol deviation.
- Progressive disease.
- Symptomatic deterioration.
- Confirmed pregnancy.
- Study terminated by sponsor.
- Withdrawal by patient.
- Lost to follow-up.
- Other.

Once study drug has been discontinued, all study procedures outlined for the EOT visit will be completed as specified in the SOE ([Appendix A](#)). The primary reason for study drug discontinuation will be recorded on the eCRF.

In the case of study termination by the sponsor, eligible patients may have continued access to modakafusp alfa as described in Section [6.5](#).

Only patients who are withdrawn from treatment during Cycle 1 during the safety lead-in for reasons other than DLT will be replaced.

Note that some patients may discontinue study drug for reasons other than progressive disease before completing the full treatment course; these patients will remain in the study for posttreatment assessments as outlined in the SOE ([Appendix A](#)) until progressive disease occurs.

## **9.9      Withdrawal of Patients From Study**

A patient may be withdrawn from the study for any of the following reasons:

- Lost to follow-up.
- Study terminated by sponsor.
- Withdrawal by subject.
- Transfer of patient to a long-term safety study, single-patient investigational new drug application, or similar program.
- Death.
- Other.

The consequence of study withdrawal is that no new information will be collected from the withdrawn patient and added to the existing data or any database.

## **9.10 Study Compliance**

Study drug will be administered or dispensed only to eligible patients under the supervision of the investigator or identified subinvestigator(s). The appropriate study personnel will maintain records of study drug receipt and dispensing.

## **9.11 Posttreatment Follow-up Assessments (PFS and OS)**

Patients who stop treatment for any reason other than progressive disease will continue to have PFS visits. The PFS visits should occur every 4 weeks from the EOT until the occurrence of progression, death, the start of subsequent systemic antineoplastic therapy, study termination, whichever occurs first. OS follow-up continues every 12 weeks until death, study termination, or patient withdrawal. Imaging tests for patients with extramedullary disease should be performed every 12 weeks or if new symptoms suggest progressive disease.

See the SOE ([Appendix A](#)) for appropriate assessments during follow-up.

NOTE: Treatment-related SAEs must be reported to the Global Pharmacovigilance department or designee. This includes deaths that the investigator considers related to study drug that occur during the posttreatment follow-up. Refer to Section [10.0](#) for details regarding definitions, documentation, and reporting of SAEs.

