## 6.3 Duration of Study

### 6.3.1 Duration of an Individual Patient's Study Participation

Patients may receive study drug treatment until they experience progressive disease, unacceptable toxicity, or other discontinuation criteria are met.

Patients who discontinue study drug treatment for reasons other than progressive disease will continue PFS follow-up every 4 weeks from the end of treatment (EOT) visit until the occurrence of progressive disease, death, the start of subsequent systemic antineoplastic therapy, study termination, whichever occurs first. OS follow-up continues every 12 weeks until death, study termination, or patient withdrawal.

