#### **9.5.7      Concomitant Medications and Procedures**

Any prior or concomitant medication a patient has had from signing of the ICF through 30 (+10) days after the last dose of study drug treatment (modakafusp alfa and/or daratumumab SC) or the start of subsequent systemic anticancer therapy, whichever occurs first, will be recorded on the eCRF. Trade name and international nonproprietary name (if available), indication, and start and end dates of the administered medication will be recorded. Medications used by the patient and therapeutic procedures (including any transfusion) completed by the patient will be recorded in the eCRF. See Sections 8.7 and 8.8 regarding medications and therapies that are prohibited or allowed, respectively, during the study.

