### **DOR, DCB, Duration of Disease Control, TTP, TTNT, PFS, OS, and Duration of MRD Negativity for Patients Achieving MRD Negativity**

DOR and duration of MRD negativity are defined in Section [13.1.3.2.1](#).

DCB is defined as the time from the date of first documentation of a minimal response or better to the date of first documentation of confirmed progressive disease or death due to any cause, whichever occurs first. DCB will be calculated for only patients who achieved a minimal response or better. Patients without documentation of confirmed progressive disease or death will be censored at the date of last adequate disease assessment.

Duration of disease control is defined as the time from date of first documentation of SD or better to the date of first documentation of confirmed progressive disease or death due to any cause. Duration of disease control will be calculated for only patients who achieved SD or better. Patients without documentation of confirmed progressive disease or death will be censored at the date of last adequate disease assessment.

TTP is defined as the time from the date of randomization to the first documentation of confirmed progressive disease as defined by IMWG criteria. Patients without documentation of confirmed progression will be censored at the date of last adequate disease assessment. The analysis will be based on the ITT population.

TTNT is defined as the time from the date of first dose administration of any study drug to the date of the first dose initiation of the next line of anticancer therapy for any reason or death from any cause, whichever comes first. Patients who have not started the next-line therapy will be censored at the date last known to be alive before subsequent anticancer therapy. The analysis will be based on the safety population.

PFS is defined as the time from the date of randomization to the first documentation of confirmed progressive disease or death due to any cause, whichever occurs first. Patients without documentation of confirmed progressive disease or death will be censored at the date of last adequate disease assessment. The analysis will be based on the ITT population.

OS is defined as the time from the date of randomization to the documentation of death due to any cause. Patients without documentation of death at the time of analysis will be censored at the date last known to be alive. The analysis will be based on the ITT population.

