TTP is defined as the time the date of randomization to the first documentation of confirmed PD per IMWG criteria, or death due to PD.

TTP (months) = (earliest date of progression or death due to PD or censor – date of randomization + 1)/30.4375.

The analysis of TTP will be based on the ITT population.

TTP will be summarized using KM method. The K-M curves, the 25th, 50th (median) and 75th percentiles, alone with associated 2-sided 95% CIs based on Brookmeyer and Crowley method, and the K-M probability estimates with 95% CIs at 3, 6, 9 and 12 months (or later time points if applicable) will be presented. The number of patients with events and the number of patients censored will be summarized. Sensitivity analysis based on the safety population will also be provided.

TTR

TTR is defined as the time from the date of first dose administration of any study drug to the date of first documentation of confirmed PR or better.

The analysis of TTR will include only responders (PR or better) based on the safety population. TTR will be summarized using descriptive statistics with mean and 95% CI.

TTNT

TTNT is defined as the time from the date of first dose administration of any study drug to the date of the first dose initiation of the next line of anticancer therapy for any reason or death from any cause, whichever occurs first. Patients who neither started the next-line therapy nor die will be censored at the date last known to be alive before subsequent anticancer therapy. Patients who do not have any post-baseline follow-up assessments and who have not died will be censored at the date of first dose administration.

TTNT (months) = (earliest date of next line or death or censor – date of first dose + 1)/30.4375.

The analysis of TTNT will be based on the safety population.

TTNT will be summarized using KM method. The K-M curves, the 25th, 50th (median) and 75th percentiles, alone with associated 2-sided 95% CIs based on Brookmeyer and Crowley method, and the K-M probability estimates with 95% CIs at 3, 6, 9 and 12 months (or later time points if applicable) will be presented. The number of patients with events along with the type of events (death or next line of anticancer therapy) and the number of patients censored will be summarized.

PFS

PFS is defined as the time from the date of randomization to the date of confirmed disease progression or death due to any cause, whichever occurs first.

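### Phase 2a time to next treatment: nothing requires next-line therapy to be recorded after progression, so TTNT is biased upward unless the 12-weekly survival contact captures it

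*Protocol*

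**What the plan says.** **Endpoint.** Protocol 5.2.2 lists TTNT as a phase 2a secondary endpoint. Protocol 13.1.3.2.2 starts the clock at the first study-drug administration and stops it at this point: "date of the first dose initiation of the next line of anticancer therapy for any reason or death from any cause". SAP 6.6.2.2 repeats the definition, with the event being "next line of anticancer therapy for any reason or death from any cause, whichever occurs first", and will count the two event types separately.

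**Censoring.** SAP 6.6.2.2: "Patients who neither started the next-line therapy nor die will be censored at the date last known to be alive before subsequent anticancer therapy". Protocol 13.1.3.2.2 has essentially the same rule.

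**Sources of a next-line start date:**

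- *Medication recording.* Protocol 9.5.7 runs it from consent to 30 (+10) days after the last dose, "or the start of subsequent systemic anticancer therapy, whichever occurs first, will be recorded on the eCRF".
- *EOT visit.* Appendix A Table 4 sets it at 30 (+10) days after the last dose, or at the start of a new systemic therapy if that is earlier.
- *PFS visits.* Protocol 6.3.1: "Patients who discontinue study drug treatment for reasons other than progressive disease will continue PFS follow-up every 4 weeks". They end at progression, death, new systemic therapy or study termination.
- *Survival contact.* Protocol 9.11: "OS follow-up continues every 12 weeks until death, study termination, or patient withdrawal". Its content is not stated. Section 9.11 refers to Appendix A for follow-up assessments, and Table 4 has no row for subsequent anticancer therapy.

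**The concern.** Progression is a common reason to start a new line of therapy, so patients who progress can be expected to supply many of the TTNT events. They are also the patients for whom the protocol stops asking. One who stops for progression has no PFS visits; one who stops for another reason leaves PFS visits on progressing. In both cases only the survival contact remains once the EOT visit is past.

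The SAP censoring rule then treats a patient known to be alive as a patient known to be free of next-line therapy. If a start is not recorded, the patient's TTNT becomes time to death or to last known alive. The error can only lengthen TTNT, the curve moves towards overall survival, and analysts cannot recover dates that sites were never asked for.

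**Working it through.** **The plan's own figures.** None concerns TTNT. The precision figures for 20 patients per arm (Protocol 13.2, SAP 4.0) reproduce: exact 95% limits at 12, 14 and 16 of 20 are (0.361, 0.809), (0.457, 0.881) and (0.563, 0.943), and 1 − (1 − p)^20 gives 64%, 88%, 96% and 99%. They do not bear on this point.

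**Step 1. Which starts are secured by the text?**

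| Situation at next-line start | Is the start identified? | Basis |
|---|---|---|
| Up to the EOT visit, any patient | Yes | The start brings EOT forward and closes medication recording |
| After EOT, stopped for another reason, not yet progressed | Yes | 4-weekly PFS visits run until new therapy starts |
| After EOT, stopped for progression | Not required | Survival contact only, content unstated |
| After EOT, progressed during PFS follow-up | Not required | PFS visits ended at progression |

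The gap is the last two rows.

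**Step 2. Direction.** Correct value: min(next-line start, death), censored at last follow-up. Value when the start is not recorded: death, or censoring at last known alive. The second is never shorter. The excess per patient is the time from next-line start to death or last contact.

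**Step 3. Illustrative size.** From the documents: about 60 months' total duration and up to 18 months' enrollment, giving administrative censoring at 42 to 60 months; and day 40 as the latest EOT date, 40/30.4375 = 1.31 months after the last dose. Assumed, because the documents give none of them: median time on treatment 6, 12 or 18 months; median gap to next line 0.5, 1, 2 or 3 months; median survival after stopping 12 or 24 months; share stopping for reasons other than progression 0% or 25%. Times are exponential. That is 3 × 4 × 2 × 2 = 48 scenarios, each simulated with 200,000 patients. Starts beyond day 40 are treated as lost if the patient stopped for progression, which supposes that the survival contact captures none of them. All starts in other patients are kept.

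Hand check of the share lost when every patient stops for progression: 0.5^(1.31/median gap). A gap of 0.5 gives 0.16, 1 gives 0.40 and 3 gives 0.74. The simulation gives 0.15 to 0.16, 0.37 to 0.39 and 0.68 to 0.71; it is slightly lower because it counts only starts that precede death and end of follow-up.

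| Treatment / gap / survival (median months), non-progression stops | Starts lost | Median TTNT, all recorded | Median TTNT, starts lost | Ratio |
|---|---|---|---|---|
| 18 / 0.5 / 12, 25% | 11% | 18.6 | 20.3 | 1.09 |
| 12 / 1 / 24, 25% | 29% | 13.4 | 18.6 | 1.39 |
| 12 / 2 / 24, 25% | 45% | 14.9 | 24.0 | 1.61 |
| 6 / 3 / 24, 0% | 71% | 10.2 | 23.8 | 2.33 |

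The first and last rows have the smallest and largest ratios. The shift was upward in all 48 scenarios.

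**The case against.** The strongest reply is that silence does not prove omission. Table 4 has no row for survival status either, yet OS is an endpoint with a scheduled contact, so the schedule plainly does not itemise that contact. The SAP presupposes the date: it counts next-line events for TTNT and uses subsequent therapy in response confirmation, the response window and PFS censoring. The case report form and data management plan are not among the documents, and one footnote to Tables 3 and 4 is blacked out. A form field may well exist.

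This reply stands against three readings that a reader might infer.

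- *That TTNT is overstated as a matter of fact.* The documents show a requirement that is missing, not data that are missing.
- *That every start after the EOT visit is lost.* Patients who stop for reasons other than progression are seen every 4 weeks until new therapy starts, so starts before progression are identified.
- *That the empty survival column shows that nothing is collected, in phase 1 as well.* The contact's content is simply unstated, and TTNT is not a phase 1 endpoint.

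The reply does not dispose of the point. An SAP that expects a date does not instruct sites to ask for it, and the absence of a row does not depend on how the schedule's columns are read. The censoring rule needs correcting even if the field exists. Its closing qualifier about preceding subsequent therapy might be meant as last known free of therapy, but it has no effect for a patient with no recorded start.

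On weight, TTNT is descriptive, with no hypothesis, decision rule or comparison of arms. Appendix G records a sponsor decision not to proceed to phase 2a, although the amendment confirming it was not implemented and the current text keeps both phase 2a and TTNT.

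**Conclusion.** The point holds in conditional form. For phase 2a patients who progress and start a next line after the EOT visit, no provision in either document requires that start to be recorded. Unless the survival contact captures it, the SAP rule moves these patients to death or last known alive and biases TTNT upward.

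The direction follows from the definitions. The size does not: the documents give no gap to next line, post-progression survival or reasons for stopping. The ranges shown (11% to 71% of starts lost, median multiplied by about 1.1 to 2.3) rest wholly on the stated assumptions and on no affected start being captured. The consequence is a possibly misleading descriptive secondary endpoint. It is worth correcting because the error runs one way, cannot be repaired at analysis and is cheap to prevent.

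**What to change.** 1. **Appendix A Table 4:** add a row, *First subsequent anticancer therapy (regimen, start date)*, marked at EOT, each PFS visit and each 12-weekly survival contact.
2. **Protocol 9.11:** state that survival follow-up records this item for all patients, including those who stopped for progression.
3. **SAP 6.6.2.2:** censor TTNT at the last contact at which absence of next-line therapy was confirmed, and align the matching sentence in Protocol 13.1.3.2.2.

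No new visits are needed. The cost is one more data item at contacts already planned (none, if the form already has it) and slightly earlier censoring for some patients.
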